8.2.2. Acceptance Criteria

- Mean error of ≤ 5 mmHg with a standard deviation of ≤ 8 mmHg.

Per *ISO 81060-2-2018 Non-invasive sphygmomanometers- Part 2: Clinical investigation of intermittent automated measurement type*, the mean value of the errors for systolic and diastolic blood pressures shall be within or equal to 5.0 mmHg with an experimental standard deviation no greater than 8.0 mmHg. The validation of Mean Arterial Pressure (MAP) for Masimo INVSENSOR00073 shall follow these requirements.

8.2.3. Data Exclusion Criteria

The following data exclusion criteria will be applied before statistical analysis.

- Either reference or test device malfunctions and/or provides inconsistent values or not values.
- Discontinuities and abrupt dropouts due to device failure.
- Any invasive systolic blood pressure change greater than [REDACTED], or diastolic blood pressure changes greater than [REDACTED] during or before determination by the sphygmomanometer-under-test.
[REDACTED] Diastolic blood pressure outside of the Masimo INVSENSOR00073 specifications of [REDACTED]
- Systolic blood pressure outside of the Masimo INVSENSOR00073 specifications of [REDACTED]

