5.2.1. Risks Associated with the Study Devices

The noninvasive devices used in this study are similar in technology and design to commercially available FDA-cleared devices and hence pose minimal risk to subjects. A *Clinical Investigation Risk Assessment* has been conducted and documented where relevant biological, chemical, electrical, and mechanical hazards associated with Masimo INVSENSOR00073 were identified and mitigated as used in this clinical investigation. Refer to the *Investigator Brochure (IB)* and/or *Operator's Manual* for full description of warnings and cautions and instructions.

There is a risk of temporary discomfort to subjects at the blood pressure cuff placement location, including temporary skin irritation, redness, and itching. In the absence of intact skin (e.g., cuts or abrasions) at or near the application site, the subject will be disqualified from the study to avoid potential discomfort.

Device warning labels are as follows:

- Frequently check the blood pressure monitoring site to ensure adequate circulation to prevent patient injury.

- Do not apply the cuff to a limb that is on the same side of a mastectomy.
- Do not use or stop blood pressure measurements if the patient appears to be affected by the pressurization of the cuff due to a physical condition (e.g., pregnant, pre-eclamptic).
- Avoid too frequent blood pressure measurements to prevent injury to the patient due to blood flow interference.
- Do not attach the cuff to a limb being used for IV infusions or any other intravascular access, therapy or an arterio-venous (A-V) shunt. The cuff inflation can temporarily block blood flow, potentially causing harm to the patient.
- Before applying the cuff on the patient, confirm the cuff size is appropriate.
- When a blood pressure measurement error code occurs, any blood pressure values reported should be disregarded.
- Do not apply the blood pressure cuff over a wound to avoid further injury.
- A compressed or kinked connection hose may cause continuous cuff pressure resulting in blood flow interference and potentially harmful injury to the patient.

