7.6.3. Study Procedures

7.6.3.1. Participant Preparation

7.6.3.1.1. General Preparation for Blood Pressure Measurement

Study staff will check with the study participant to ensure that the subject has emptied his/her bladder. The subject will be asked to be seated in a relaxed position on a chair, with his/her feet uncrossed and on the floor, and back supported for approximately 5 minutes. Study staff will explain to the subject that it is imperative that the subject refrains from motion and talking during the measurement. The subject will be asked to remove article(s) of clothing covering the location of cuff placement.

7.6.3.1.1.1. Cuff Size Selection

Circumference of both arms will be measured at the cuff placement location, to ensure the correct cuff size is used, such that the bladder encircles 80% of the arm.⁽⁹⁾ Masimo INVSENSOR00073 comes with three cuff sizes as follows:

Small adult (20-26 cm)

Adult (25-34 cm)

Large Adult (32-43 cm).

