7.6.3.3. Blood Pressure Variations Procedure

During the blood pressure variations procedure, participants will be administered continuous infusions containing vasoactive medications. There will be two study types:

[figure not shown]
[figure not shown]
Induced controlled hypertension (increased blood pressure)

Induced controlled hypotension (decreased blood pressure)

Both study types will involve the use of a primary drug to elicit the desired blood pressure change.

Vasoactive Medication

[figure not shown]
[figure not shown]
 will be used as the primary drug to induce hypertension (increased blood pressure) and  will be used to induce hypotension (decreased blood pressure).

Study Title: Validation Study of Mean Arterial Pressure (MAP) Parameter of Masimo
INVSENSOR00073

Revision: 

Safety drugs will be used to counteract the effects of the primary drugs when deemed necessary by the presiding clinician. Table 1 outlines the possible primary and safety drug choices based on the pressure variation study type.

Table 1. Drugs allowed for pharmacological variations of blood pressure variation studies.

Type of Pressure Variation Study	Primary Drug	Safety Drug
		
		

Blood Pressure Safety Limits

Medication-induced blood pressure variation studies have strict pressure variation limits to ensure the subject's blood pressure stays within a safe range. Tables 2 and 3 below outline the maximum allowable pressure variations for each study type. If the blood pressure limits are reached or exceeded, drug infusion will be stopped immediately, and the subject will be monitored as blood pressure returns to the baseline values. The study may be continued if the subject is comfortable, and clinicians deem it is safe to proceed.

Target blood pressure changes must be determined prior to starting the study for each subject. The selected variation must be the lesser of the percent and absolute changes indicated in Table 2, provided the selected variation does not violate the limits established in Table 3. Vasoactive medications are titrated based upon the arterial line-derived mean arterial pressure (MAP) reading. Blood pressures must remain within the limits defined in Table 3 for the duration of the procedure.

Table 2. Maximum allowed pressure variations for each study type. Target pressure variations are calculated based on mean arterial pressure (MAP)

Study Type	Percent Change From Baseline MAP	Absolute Change From Baseline MAP
Controlled Hypertension		

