The reference MAP will be read from the values displayed on the reference invasive blood pressure monitoring equipment. Since the recording is not interrupted due to cuff inflation, the reference blood pressure ranges shall be determined from the recording of the invasive blood pressure for a duration of at least 30 seconds that includes the period of determination of INVSENSOR00073. Specifically, 30 seconds of reference recordings prior to the determination of INVSENSOR00073 will be used. Reference recordings and determination of Masimo INVSENSOR00073 will be synchronized based on the time stamp of the data acquisition device.

For the sphygmomanometer-under-test, the mean value of the errors \bar{x}_n and experimental standard deviation s_n of the n individual paired determinations of the Masimo INVSENSOR00073 for all subjects shall be calculated according to the formulas (4) and (5) below:

$$(4) \text{ Mean Error: } \bar{x}_n = \frac{1}{n} \times \sum_{i=1}^n x_i$$

$$(5) \text{ Standard Deviation: } s_n = \sqrt{\frac{1}{n-1} \times \sum_{i=1}^n (x_i - \bar{x}_n)^2},$$

where x_i is the error of the i^{th} individual determination, n is the total number of determinations, and i is the index for the individual determination.

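### Section 8.2.3 lets a pair be dropped because the test device gave inconsistent values, without defining the term or withholding the paired arterial value, so exclusion could depend on the error being validated

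*Combined protocol and SAP*

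**What the plan says.** Section 8.2.3 states that "The following data exclusion criteria will be applied before statistical analysis". Its first ground is that "Either reference or test device malfunctions and/or provides inconsistent values or not values". The other grounds are signal discontinuity from device failure, invasive pressure changes above redacted limits, and pressures outside the device's specifications. The first ground carries no redaction.

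Section 8.2.1 computes the mean error and SD by formulas (4) and (5) over the individual paired determinations, which means the pairs left after exclusion. Section 8.2.2 compares the two point estimates with fixed limits: "Mean error of ≤ 5 mmHg with a standard deviation of ≤ 8 mmHg".

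On the arterial value, Section 8.2.1 says "The reference MAP will be read from the values displayed on the reference invasive blood pressure monitoring equipment", and Section 7.6.3.3 says "Vasoactive medications are titrated based upon the arterial line-derived mean arterial pressure (MAP) reading".

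Three statements elsewhere bear on what a faulty test reading might be. The device warnings in Section 5.2.1 say "When a blood pressure measurement error code occurs, any blood pressure values reported should be disregarded" and "A compressed or kinked connection hose may cause continuous cuff pressure resulting in blood flow interference". Section 7.6.3.1.1 has staff tell the subject that "it is imperative that the subject refrains from motion and talking during the measurement". Section 8.2.3 refers to none of them.

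**The concern.** The outcome is the test reading minus the arterial reading, corrected for lateral difference. A test reading far from the arterial line is a large error and, on one reading that the text allows, also an inconsistent value. An exclusion rule that the outcome itself can trigger may remove the evidence that the acceptance limit is meant to weigh. The same holds for erratic test readings, since scatter is what the SD measures.

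The plan gives no comparator, no threshold and no decision-maker, and does not require the decision to be made without the arterial value. That value is on display and guides the infusion, so masking to it cannot be presumed. No analysis puts the excluded readings back. At stake is whether an observed SD of 8 mmHg or less describes the device or the device after selection.

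**Working it through.** **1. The plan's own figure.** Section 8.1 requires 15 subjects with at most 10 readings each: 15 × 10 = 150 valid points, as stated. Section 7.5.3 plans about 20 subjects, so 20 × 10 = 200 pairs is used below as a convenient full data set. The plan states no expected SD or power, so there is nothing further to reproduce.

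**2. Inputs.** From Section 8.2.2: pass if |mean error| ≤ 5 and SD ≤ 8 mmHg. Assumed, because the documents give no values: true SD 7.0 to 10.0, zero mean error, normal errors, within-subject correlation 0 or 0.5, and the number and type of readings dropped.

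**3. Error-blind exclusion.** With independent normal errors, (n − 1)s²/σ² follows a chi-square distribution on n − 1 degrees of freedom. At σ = 9.0:
- n = 200: P(χ²₁₉₉ ≤ 199 × 64/81 = 157.2) = 0.013.
- n = 190, after 10 are removed at random: P(χ²₁₈₉ ≤ 189 × 64/81 = 149.3) = 0.015.

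Exclusion unrelated to the error leaves the pass probability essentially unchanged.

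**4. Exclusion of the largest errors.** If a fraction f with the largest absolute errors is removed, a normal SD is multiplied by √(1 − 2cφ(c)/(1 − f)), where c is the cut-off in SD units. For f = 0.05 (10 of 200), c = 1.960 and φ(c) = 0.05845. The factor is √(1 − 2 × 1.960 × 0.05845/0.95) = 0.871, so a true SD of 9.0 shows as 9.0 × 0.871 = 7.84.

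**5. Pass probabilities by simulation** (20 subjects × 10 readings, 20,000 runs per setting). Removing the largest errors is the worst case; drawing at random from the worst 20% represents partial targeting.

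| True SD | Correlation | Dropped of 200 | Error-blind | Random from worst 20% | Largest errors |
|---|---|---|---|---|---|
| 9.0 | 0 | 3 | 0.01 | 0.03 | 0.11 |
| 9.0 | 0 | 5 | 0.01–0.02 | 0.05 | 0.24 |
| 9.0 | 0 | 10 | 0.01–0.02 | 0.16 | 0.65 |
| 9.0 | 0.5 | 10 | 0.14 | 0.34 | 0.64 |
| 8.5 | 0 | 6 | 0.13 | 0.32 | 0.73 |
| 10.0 | 0 | 10 | 0.00 | 0.00 | 0.06 |
| 10.0 | 0.5 | 10 | 0.01 | 0.06 | 0.22 |
| 7.0 | 0 | 10 | 1.00 | 1.00 | 1.00 |
| 7.0 | 0.5 | 10 | 0.96 | 0.99 | 1.00 |

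**6. Why the reason for exclusion matters.** Take 198 readings with SD 7.5 and zero mean, plus two readings with an error of +30 mmHg. The overall SD is √((198 × 7.5² + 2 × 30²)/200 − 0.3²) = 8.04, a fail. Without the two it is 7.5, a pass. If the hose was kinked, removing them is right. If the device was simply wrong, removing them hides the failure. The present wording does not separate these cases.

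**The case against.** The strongest reply is that the harmful reading is the less natural one. The bullet covers either device, and its other terms describe faults. Section 9.4 also sets inconsistent data points beside missing ones when it describes queries on case report forms, which is a data-quality sense, and Section 9.3 has the monitor query inconsistencies. An artefact ground has a real use: motion, talking or a kinked hose could give a number without an error code. This stands and makes artefact the likelier intent. But Sections 9.3 and 9.4 concern form entries and do not define the exclusion rule.

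Second, a reader might infer that session staff see both values and can discard discordant pairs on the spot. The documents do not support that. They show that the arterial MAP is visible, not that the test value is; Section 3 allows the module to feed a laptop for data collection. The analysed error also needs a synchronised 30-second arterial recording and the lateral correction. What remains is that whoever applies Section 8.2.3 is not required to be without the arterial value or the error.

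Third, existing controls might seem enough. Applying exclusions before analysis fixes only the order. De-identification (Section 9.1) hides identity, not the paired value. The audit trail (Section 9.3) and deficiency recording (Section 15.4) leave a record but set no criterion. The error-code warning is objective but is not tied to Section 8.2.3.

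Fourth, the 150-point minimum might be read as a cap on exclusions. It is not a firm one: enrolment is approximate (7.5.3), withdrawn subjects may be replaced (7.5.4.2), the sample may be increased (8.2.4), and completion depends on reaching enough quality data points (7.3).

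Finally, the plan follows a standard that may define a valid determination. That cannot be checked from the documents.

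**Conclusion.** The gap in the wording is certain; its use to remove discordant readings is not shown. It would be wrong to infer that the sponsor plans to trim large errors, or that 0.65 is the plan's false-pass probability. That figure needs a true SD of 9.0, independent normal errors, zero mean error and deletion of exactly the ten largest errors. Dropping three or five under the same assumptions gives about 0.11 or 0.24, and partial targeting gives about 0.03 and 0.05, against 0.01 to 0.02 with error-blind exclusion.

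The size depends on the assumed SD, correlation, number dropped and targeting. The direction of the bias in the SD under error-driven exclusion does not. A device well inside the limit is essentially unaffected, and one at a true SD of 10 rarely passes after ten exclusions. The weakness bites just above 8 mmHg, where the limit has to discriminate. Because the remedy is cheap, this should be fixed before exclusions are applied.

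**What to change.** In Section 8.2.3, replace inconsistent values for the test device with objective grounds:
- a device error code;
- no value;
- a documented malfunction;
- artefact such as motion, talking or a kinked hose, recorded at the time of measurement.

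Require these to be decided without reference to the paired arterial value or the error. Decide reference-side exclusions from the arterial recording alone, before pairing. Report exclusions by reason and by subject.

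Beside the main result, repeat formulas (4) and (5) and the 5/8 mmHg check as a sensitivity analysis, restoring only the test readings without an error code that were excluded as inconsistent or artefact. Pairs excluded for unstable invasive pressure or out-of-specification pressure stay excluded. List the restored readings if the two verdicts differ. The repeat should not replace the main analysis, because it deliberately includes artefact.

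The cost is SAP wording, a time-stamped artefact field and reason code on the case report form, and one further run of the same calculation. No extra subjects or procedures are needed. The downside is that the reported SD may be larger and that unrecorded artefact stays in the main analysis. As an illustration, assume a true SD of 7 and six artefacts of SD 25 among 200 independent readings. The pass probability is 1.00 if all six are documented and excluded, 0.79 if three are, and 0.48 if none are (0.95, 0.76 and 0.51 at correlation 0.5). Prompt recording therefore matters, and artefact should remain a documented ground rather than be deleted.

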8.2.4. Expected Dropouts and Study Participant Replacement

Subjects may not complete the study for various reasons, such as a clinical screening test failure, at the investigator's or study staff's discretion, or because the subject does not want to continue the study. Accordingly, the sample size per group may be increased to account for dropout rates during the study.

9. DATA MANAGEMENT

9.1. Data Management and Confidentiality

All documents associated with this protocol will be securely stored in a physical location or on password-protected computers. The confidentiality and retention of these documents will be protected to the extent provided and required by the law. All data will be de-identified before any statistical analysis. Only de-identified data will be shared with Masimo for research purposes stated in this protocol. Data collected by the eCRF data capture software will be shared with Masimo via a secure, password-protected server that only study staff, and Masimo study team members will have access to. Data will be retained for a minimum of two years following completion of the final analysis.

9.2. Source Documents

Source data is all information, original records of clinical findings, observations, or other activities in a clinical trial necessary for the reconstruction and evaluation of the trial. Source data are contained in source documents. Examples of these original documents and data records include hospital records, clinical and office charts, laboratory notes,

memoranda, recorded data from automated instruments, and copies or transcriptions certified after verification as being accurate and complete.

9.3. Case Report Forms

The site shall capture study data in case report forms (CRFs) for each subject enrolled, to be provided to the sponsor. CRFs may be in paper or electronic format through electronic data capture (EDC) software. Masimo shall ensure that systems used for electronic CRFs are compliant with the requirements of 21 CFR Part 11 and ISO / IEC 27001 certification. The CRFs will be completed and signed by the PI or delegate. This also applies to those subjects who fail to complete the study.

If a subject withdraws from the study, the reason must be noted on the CRF. The eCRFs are to be completed on an ongoing (weekly) basis. CRF entries and corrections will only be performed by study site staff, authorized by the investigator. For paper CRFs, entries and corrections to the CRF will be made following good documentation practices (GDP).

The CRF may include the following information, including but not limited to inclusion/exclusion criteria, whether subject consent was obtained before start of study, demographic information, device readings, and if occurrence of any adverse event, protocol deviation, and device deficiencies, etc. The CRFs will be signed by the PI or delegate to attest that the data are complete and accurate.

CRF entries will be checked by the study monitor and any errors or inconsistencies will be queried to the site on an ongoing basis. Any changes made within an electronic CRF will be tracked by audit trail. Any changes on a paper CRF will be made directly on the CRF and will be initialed and dated by the person making the change. Query resolution will be assessed and confirmed by the study monitor during site visit.

9.4. Data Transfer and Storage

Original paper CRFs will be stored in a secure location at the site. Copy of the original paper CRFs may be scanned and sent to sponsor. If using electronic CRFs, the site staff will be assigned unique usernames and passwords for data security. Final copies of the electronic CRFs in EDC are stored on a secure server.

Only authorized sponsor personnel will have access to study data and will move it to a secure and backed-up drive at Masimo.

CRFs will be checked for completeness and if there are inconsistent or missing data points, queries will be generated. If delegated study staff are to correct the paper CRF, they shall follow GDP practices to strike through old entry, add in new entry, initial and date it, and provide the corrected information to sponsor. Corrections made to electronic CRFs will be tracked by audit trail and require PI or delegate sign-off.

9.5. Record Retention

Study data will be retained for the necessary period of time as required by the institution's regulations. Study records shall be retained for a minimum of two years after study closure. The institution's own retention policies and regulations may apply in addition to the minimal requirement.

10. AMENDMENTS TO THE CLINICAL INVESTIGATION PLAN

Any changes made to the clinical investigational plan/study protocol will be documented by way of an amendment. Before submitting a protocol amendment to the IRB, the protocol amendment must be agreed upon and signed by both

the PI and the sponsor. The protocol amendment will be submitted to the IRB for approval. At a minimum, a redline version and a clean version of the new protocol amendment will be kept on file by the PI and the sponsor. Protocol amendments will need to be version controlled. Both PI and sponsor will retain the IRB approval letter as confirmation that the protocol amendment was approved.

11. DEVIATIONS FROM CLINICAL INVESTIGATION PLAN

Deviations from the protocol must receive both sponsor and the investigator's IRB/ethics committee approval before they are initiated, with the exception that under emergency circumstances, deviations from the *Clinical Investigation Plan* to protect the rights, safety and well-being of human subjects may proceed without prior approval of the sponsor or the IRB/ethics committee.

Any protocol deviations initiated without sponsor and the investigator's IRB/ethics committee approval that may affect the scientific soundness of the study, or affect the rights, safety, or welfare of study subjects, must be documented and reported to the sponsor and to the investigator's IRB/ethics committee as soon as a possible, but no later than 5 working days after the occurrence of the protocol deviation. In addition to documenting deviations on the CRF, the *Protocol Deviation Form* may also be used. If protocol deviations continue to occur frequently at a study site, a corrective and preventive action (CAPA) may be opened by the sponsor.

Withdrawal of IRB approval: An investigator shall report to the sponsor a withdrawal of approval by the investigator's reviewing IRB as soon as possible, but no later than five working days of the IRB notification of withdrawal of approval.

